13. SAFETY ANALYSES

All safety analyses will be performed on the Safety population using the following common rules:

- The baseline value is defined generally as the last available value before the first administration of study drug
- The analysis of the safety variables will be descriptive, and no hypothesis testing is planned
- The safety analysis will focus on the treatment-emergent period, which is defined as the time from the first administration of study drug to the last administration of study drug + 56 days.

13.1. Adverse Events

AEs will be mapped to system organ classes and preferred terms using the Medical Dictionary for Regulatory Activities (MedDRA v21.0). AEs will be monitored during the study and the data analyzed with respect to overall incidence as well as severity and potential relationship of AEs to study medication. AEs with onset during the treatment-emergent period or with an onset before the first dose of study medication that increases in severity or becomes serious during the treatment-emergent period, will be considered treatment-emergent.

Adverse event incidence tables will present the number (n) and percentage (%) of subjects experiencing at least one treatment-emergent AE (TEAE) by system organ class (SOC) and preferred term (PT). Multiple occurrences of the same event in the same patient will be counted only once in the tables. The denominator for computation of percentages is the safety population within each treatment group. In addition, the adverse event incident table will also be presented by SOC, PT, and severity grade. When there are multiple occurrences of the same event in the same patient, only the most severe one will be included in the tables.

Adverse event incidence tables will be provided by treatment group for all types of TEAEs: all TEAEs, all treatment-emergent serious AEs, drug related AEs, AEs of Special Interest (AESI; per protocol), all TEAEs leading to permanent treatment discontinuation, and all TEAEs leading to death.

AE may also be summarized by Standardised MedDRA Queries (SMQs) deemed relevant based on AESIs and SAEs observed in the study.

A by-subject listing of all AEs, SAEs, and TEAEs leading to treatment discontinuation will also be provided.

Deaths

The following deaths summaries will be generated in a summary table and listed in a by-subject data listing:

- Number and percent of subjects who died by study period (TEAE, on-study) summarized on the safety population by treatment received
- Death in non-randomized subjects or randomized and not treated subjects
- TEAE leading to death (death as an outcome on the AE eCRF page as reported by the investigator) by primary SOC and PT showing number and percent of subjects

Pregnancy

The following pregnancy information will be provided in a by-subject data listing:

- Number of subjects or partners of subjects who became pregnant summarized by treatment received
- Outcomes of the pregnancies and analysis of the outcomes
- TEAE experienced during the pregnancy by primary SOC and PT showing the number and percent of subjects

Overdose

If overdoses occur, the following overdose information will be provided in a by-subject data listing:

- Number of subjects who experienced overdose summarized by treatment received
- Analysis of the cause and occurrence of the overdose
- TEAE, if any, experienced during the overdose by primary SOC, high-level group term, high-level term, and PT showing the number and percent of subjects

13.2. 12-lead Electrocardiogram

The RR, PR, QRS, and QT intervals will be measured and read by a central laboratory. HR will be calculated as $60/(RR \times 1000)$ (with RR expressed in msec) and rounded to the nearest integer.

Correction for Heart Rate

Corrected QT interval (QTc) will be calculated using the manually over-read QT values. Each individual ECG QT value will be corrected for HR. The measured QT data will be corrected for HR using QTcF as per the following formulae/method (with QT, RR and QTc expressed in msec):

Fridericia's Correction:

$$QTcF = \frac{QT}{(RR/1000)^{(1/3)}}$$

ECG Numeric Variables

HR, PR, QRS, and QTcF will be summarized using descriptive statistics. The change from baseline of these ECG parameters at each time point will be listed for each patient. For each time point of measurement, the changes from baseline will be summarized using descriptive statistics.

Categorical Analysis

The incidence count and percentage of subjects with any postdose QTcF values of > 450 msec, > 480 msec, and > 500 msec will be tabulated for all subjects. Subjects with QTc values > 500 msec will be listed with corresponding baseline values, Δ QTcF, and baseline and treatment HR. The incidence count and percentage of subjects with Δ QTcF increase from baseline of > 30 msec and > 60 msec will be tabulated.

Morphology Findings

ECG morphologies for each patient will be listed.

Concentration-QTc Analyses

The concentration-QTc relationship will first be evaluated by a scatterplot of time-matched QTcF and concentration data to investigate any potential delayed or sustained effects and to explore the shape of the relationship. Linear or nonlinear mixed models may then be applied, if appropriate, to estimate the slope and 95% CI of the concentration-QTc relationship. For linear mixed effects models, concentration and sex will be included as fixed effects, subject as random effect, and compound symmetry will be implemented for the variance-covariance structure.

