### **9.3.3        *12-lead ECG***

Twelve-lead ECG evaluations will be performed after 10 minutes of rest at Screening and at all onsite study visits except the Week 6 visit. All ECG data will be sent to a central cardiac laboratory.

On Day 1, ECG will be performed predose

The investigator will judge the overall interpretation as normal or abnormal with clinical significance. The investigator will review the ECG and correlate abnormal findings with any other clinical findings, participant's medical history, and laboratory data to determine the clinical importance of the finding.

The investigator may add extra 12-lead ECG safety assessments if there are any abnormal findings or if the investigator considers it is required for any other safety reason. These assessments should be recorded as an unscheduled assessment.

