### **9.3.5            *Vital Signs***

Vital signs, including temperature, HR, respiratory rate, and blood pressure (BP), will be obtained at Screening, ET (if applicable), Week 16 (end of treatment), and Week 24 (EOS). At all other onsite visits except Week 6, only HR and BP are required. If PK sampling is conducted at a visit, vital signs should be collected before PK sampling. Vital signs should be taken with the participant in the same position at all visits. BP should be taken via an automated recorder after the participant rests for at least 5 minutes.

Vital signs will be taken prior to dosing. Refer to the Study Reference Manual for additional details.

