#### 12.3.8.2 12-lead Electrocardiogram

The RR, PR, QRS, and QT intervals will be measured and read by a central laboratory. HR will be calculated as  $60/(RR \times 1000)$  (with RR expressed in msec) and rounded to the nearest integer.

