#### *Correction for Heart Rate*

Corrected QT interval (QTc) will be calculated using the manually over-read QT values. Each individual ECG QT value will be corrected for HR. The measured QT data will be corrected for HR using QTcF as per the following formulae/method (with QT, RR and QTc expressed in msec):

Fridericia's Correction:

$$QTcF = \frac{QT}{(RR/1000)^{1/3}}$$

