13.4. Vital Signs Data

The summary statistics (including number, mean, median, SD, minimum and maximum) of all vital signs variables (values and changes from baseline) will be calculated for each visit (baseline and post-baseline time points) and presented by treatment group.

Shift tables reflecting changes from baseline may be presented in lieu of descriptive statistics of changes from baseline.

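### The ECG heart-rate formula multiplies RR in msec by 1000 instead of dividing, so coded literally every ECG heart rate rounds to 0 bpm

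*SAP*

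**What the plan says.** SAP 13.2 has the central laboratory measure RR, PR, QRS and QT, and then derives heart rate as "60/(RR \times 1000)$ (with RR expressed in msec) and rounded to the nearest integer". Protocol 12.3.8.2 prints the same expression with the same unit and rounding rule ("with RR expressed in msec) and rounded to the nearest integer").

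The Fridericia correction follows directly in both documents. It also takes RR in msec ("with QT, RR and QTc expressed in msec" in the protocol) and divides QT by the cube root of RR/1000.

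The derived heart rate is used in two places in SAP 13.2:

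- **ECG Numeric Variables:** "HR, PR, QRS, and QTcF will be summarized using descriptive statistics". Changes from baseline are listed by patient and summarised by time point.
- **Categorical Analysis:** the listing of subjects with QTc above 500 msec shows, among other columns, "QTcF, and baseline and treatment HR".

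**The concern.** Heart rate in beats per minute is 60 divided by the RR interval in seconds. To convert msec to seconds one divides by 1000. The printed formula multiplies, while the QT correction beside it divides, so the same section treats the same variable in opposite ways.

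The SAP is the specification against which programs are written and checked. Followed literally, this line would make the ECG heart-rate summaries, their changes from baseline and the heart-rate columns of the QTc listing meaningless. The listing matters most to a reader, because heart rate is the context for judging a rate-corrected QT. Safety and tolerability is the stated objective of the trial (Protocol 3.1, SAP 2.1), so these displays belong to its main purpose even though they are descriptive.

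**Working it through.** **Inputs.** The formula, the unit (msec) and the rounding rule come from SAP 13.2 and Protocol 12.3.8.2. The documents give no RR or QT values and no worked heart rate, so there is no figure of the plan's own to reproduce. The RR and QT values below are illustrative assumptions.

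**Printed formula against the correct one.**

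| RR (msec) | Printed: 60/(RR × 1000) | Rounded | Correct: 60/(RR/1000) |
|---|---|---|---|
| 300 | 0.0002 | 0 | 200 |
| 500 | 0.00012 | 0 | 120 |
| 800 | 0.000075 | 0 | 75 |
| 1000 | 0.00006 | 0 | 60 |
| 1500 | 0.00004 | 0 | 40 |
| 2000 | 0.00003 | 0 | 30 |

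The ratio of correct to printed is [60/(RR/1000)] / [60/(RR × 1000)] = 1000 × 1000 = 1,000,000, whatever the RR.

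**Could any RR give a nonzero result?** The unrounded value must reach 0.5, which needs RR ≤ 60/(0.5 × 1000) = 0.12 msec. No heart beats at that interval.

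**Is the unit label the real mistake?** If RR were entered in seconds, the printed formula over RR of 0.3 to 2 seconds would give 60/(0.3 × 1000) = 0.2 down to 60/(2 × 1000) = 0.03. Both still round to 0, so a wrong unit label does not explain it.

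**Is a bracket misplaced?** (60/RR) × 1000 equals 60000/RR and is correct. This may be how the slip arose, and it leads to the same correction.

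**Effect on one row of the QTc listing.** Take QT 470 msec and RR 800 msec. QTcF = 470/(800/1000)^(1/3) = 506 msec, so the subject is correctly listed as above 500. The heart-rate column would print 0 instead of 60000/800 = 75 bpm.

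**How far the error spreads.** QTcF is calculated from QT and RR directly, not from the derived heart rate. The QTcF thresholds, the change in QTcF, the concentration-QTc analysis and the QTcF stopping criterion in Protocol 7.5 are therefore untouched.

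A second source of heart rate exists at the same visits. ECGs are done "at Screening and at all onsite study visits except the Week 6 visit". Vital signs include heart rate at Screening, Week 16 and Week 24, and for the rest Protocol 9.3.5 says "At all other onsite visits except Week 6, only HR and BP are required". SAP 13.4 reports these separately: summary statistics for "all vital signs variables (values and changes from baseline) will be calculated for each visit". The skin patch in Protocol 9.3.4 records heart rate as well.

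**The case against.** The strongest reply is that this is a typographical slip with almost no practical consequence. The QT correction shows what was meant, and harm would need someone to code an impossible formula and then pass a table of zeros through quality control. The outputs are descriptive, with no hypothesis testing planned on safety variables. The SAP also does not say who calculates heart rate. If the central laboratory supplies it, the line may never be programmed. Finally, the SAP section on changes from protocol-defined analyses (Section 16) cannot be read in the public copy, so a correction there cannot be excluded.

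Most of this stands, and it is why the point is minor. It does not make the formula right. A programmer who notices the error must still depart from the written plan, and that departure should be documented rather than silent. If the laboratory supplies heart rate, the SAP should say so. An error in reading the PDF is unlikely: the same expression appears in both documents, while the division by 1000 in the neighbouring formula was read correctly both times.

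**Conclusion.** The formula is wrong as written in both documents, by a factor of 1,000,000, and gives 0 bpm for every physiological RR interval. The damage is conditional on literal coding. It is then confined to the ECG heart-rate summaries, their changes from baseline (listed and summarised) and the heart-rate columns of the listing of QTc above 500 msec. No QTcF result and no RR source data are affected. The arithmetic does not depend on the illustrative values chosen. Severity is minor, with high confidence.

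**What to change.** In SAP 13.2, state HR = 60/(RR/1000) = 60000/RR, with RR in msec, rounded to the nearest integer. If the central laboratory is to supply heart rate instead, say so in the same place.

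Make the matching correction in Protocol 12.3.8.2. Protocol 14.4 allows obvious errors of this kind to be corrected by Administrative Letter.

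The cost is one line in the SAP and a housekeeping correction in the protocol. No new data are needed, and no endpoint or QTcF result changes.

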4.2. Study Blinding

Patients will be randomized to 1 of 3 groups via the IXRS. All patients receive either 5 mg mavacamten or matching placebo daily from Day 1 to Week 6. Blinded dose adjustment (to 2.5,

5, 10, or 15 mg mavacamten or placebo daily) via the IXRS will begin at Week 6 based on PK measurements at Week 4. Study drug administration will occur in a double-blind manner via the IXRS such that the investigator, site staff, the pharmacist, and the patient will not know which study drug is being administered.

In addition, the Sponsor, the central and core laboratories, and clinical site monitors will be blinded to assigned treatment. Echocardiography results (eg, LVEF) performed at clinic visits will be blinded to the investigator and study staff. The 4 different doses of mavacamten and matching placebo will be identical in appearance in order to preserve the blind. Study drug (2.5, 5, 10, or 15 mg mavacamten or matching placebo) will be labeled with a unique identifying number that will be assigned to a patient through the IXRS.

Members of the pharmacovigilance team will be unblinded for suspected unexpected serious adverse reaction (SUSAR) reporting. The IDMC may also review unblinded safety and efficacy data.

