6. GENERAL STATISTICAL CONSIDERATIONS

The primary analysis will be conducted through the 16-week treatment period. Data collected through this timepoint will be cleaned and locked prior to analysis.

Once all subjects have completed their Week 24/EOS visit, all data will be cleaned and locked, and analyses using this data will be used to inform study objectives relating to follow-up safety and reversibility of drug effect.

SAS® version 9.4 or higher will be used for statistical analyses, tabulations and graphical presentations.

In general, descriptive summaries will be presented by treatment group [placebo, Group 1, Group 2, and overall active]. Summaries of continuous variables will utilize the number of subjects (N), mean, standard deviation (SD), median, minimum and maximum. Descriptive summaries for categorical variables will utilize counts and percentages. Unless otherwise stated, denominators for percentages will be the number of patients in the analysis population with non-missing variable of interest for the column of interest.

The between-group comparisons focus on the comparative performance of Group 1 (target concentration of ~200 ng/mL) vs placebo and Group 2 (target concentration of ~500 ng/mL) vs

placebo. An overall active vs placebo comparison will also be conducted where appropriate. Any statistical test will be conducted at a two-sided significance level of 0.05 using the exact method unless otherwise stated.

In general, baseline is defined as the last non-missing result on or before the first dose date, and time where applicable. For certain data types (e.g., accelerometer, PROs, cardiac rhythm monitoring, etc.), special considerations may be required; please refer to the specific data section for details. Unless otherwise noted, non-safety (ie. efficacy, PD) information displayed “by visit” will utilize analysis visits as defined by the analysis visit window as opposed to the visits at which the information was collected (ie. nominal visit). Data collected at unscheduled or early termination visits will also be mapped to analysis visits. The analysis day for purposes of the visit windows are derived as follows (reference date is the study drug initiation date for the safety population or the randomization date for the ITT population):

- If date of information is missing, analysis day cannot be calculated and leave as missing
- If date of information < reference date, analysis day = analysis date – reference date.

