^g At Screening, Week 16, and Week 24, a complete physical examination will be conducted, including a neurological examination. At Week 4, Week 8, and Week 12, an abbreviated cardiopulmonary physical examination will be conducted, with other systems assessed as directed by interval history. Physical examinations will also include height (at Screening only) and weight (at all onsite visits at which a physical examination is performed).

^h 12-lead ECGs will be performed at Screening and all onsite visits except for the Week 6 visit after 10 minutes of rest. Each time an ECG is completed, a 10-second paper ECG will be obtained and maintained in the study patient's source documentation. On Day 1, an ECG will be performed predose.

[figure not shown]
ⁱ Resting TTE should be performed prior to post-exercise stress echocardiography or CPET. Instantaneous peak LVOT gradient at rest and provoked peak LVOT gradient (Valsalva maneuver) will be assessed only at Screening.

[figure not shown]
[figure not shown]
- j After a 4-hour fast, patients will undergo a standard symptom-limited exercise test by standardized treadmill or bicycle ergometer. Instantaneous peak LVOT gradient will be assessed immediately post-exercise by TTE.
- k CPET by standardized treadmill or bicycle ergometer will be performed on both Day 1 and at Week 16/ET prior to dosing. CPET is done after a 4-hour fast. Obtain CPET with study patient in the same position at Week 16 as done on Day 1.
- l The accelerometer is to be distributed during Screening and at the Week 12 visit and retrieved at the Day 1 and Week 16 visits.
- m The cardiac monitoring adhesive skin patch is to be applied during Screening and at the Week 12 visit and retrieved at the Day 1 and Week 16 visits.
- n Blood samples for PK will be collected at all post-Screening onsite visits except for the Day 1 and Week 6 visits. The time of each blood draw will be recorded. At Week 16, a PK sample will be collected before dosing as well as within 2 hours postdose. On other PK sampling days, the PK blood samples can be taken at any time that best facilitates conduct of all scheduled study procedures. The date and time of the last dose of IMP taken prior to the PK sample collection will be recorded.
- o At Screening, the blood draw for NT-proBNP will occur prior to post-exercise stress echocardiography. At the Day 1 and Week 16 visits, the blood draw for NT-proBNP will be obtained both prior to and immediately after CPET.

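### The linear concentration-QTc model in SAP 13.2 omits baseline QTcF, which costs some precision, and its slope is not adjusted for any QTcF trend shared by all arms (minor)

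*SAP*

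**What the plan says.** SAP 13.2 (Concentration-QTc Analyses) starts with a scatterplot of time-matched QTcF and concentration. Linear or nonlinear mixed models "may then be applied, if appropriate, to estimate the slope and 95% CI of the concentration-QTc relationship". For the linear version, "concentration and sex will be included as fixed effects, subject as random effect", with a compound-symmetry covariance. The response is QTcF itself, not its change from baseline. Protocol 12.3.8.2 describes the same analysis and names no baseline or visit term either.

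The schedule bears on this in three ways (SAP Appendix A, footnotes h and n; SAP 4.2):

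- "On Day 1, an ECG will be performed predose".
- "Blood samples for PK will be collected at all post-Screening onsite visits except for the Day 1 and Week 6 visits". ECG and PK therefore coincide at Weeks 4, 8, 12, 16 and 24, and the Day 1 ECG has no PK partner.
- Both active arms start on the same dose, and blinded adjustment "via the IXRS will begin at Week 6 based on PK measurements at Week 4". Dosing ends at Week 16, and Week 24 falls about 8 weeks after the last dose.

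SAP 13.2 does not say whether the off-drug Week 24 pairs enter the model. SAP 6 says of the data locked after Week 24 that "analyses using this data will be used to inform study objectives relating to follow-up safety and reversibility of drug effect". SAP 13 runs the treatment-emergent period to "the last administration of study drug + 56 days". On who is analysed, SAP 13 states: "All safety analyses will be performed on the Safety population using the following common rules". SAP 13.2 does not say whether placebo records enter the regression at concentration zero.

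**The concern.** A predose QTcF carries information about each participant's own level. A model for post-dose QTcF that leaves it out estimates the slope less precisely than the collected data allow.

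Concentration also moves with calendar time: one level at Week 4, another from Week 8 to Week 16, and presumably near zero at Week 24. If QTcF drifted for any reason common to all arms, part of that drift would load onto the concentration slope. Placebo records at zero reduce this but do not remove it, because much of the information on the slope comes from within-subject changes over visits.

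At stake are the slope and its 95% CI, which are the planned estimate of how QTcF moves with concentration.

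**Working it through.** **Inputs from the documents.** About 20 participants per arm, 1:1:1 (SAP 4.1 and 5). Targets of about 200 and 500 ng/mL (SAP 3). ECG/PK pairs at Weeks 4, 8, 12, 16 and 24. The plan gives no precision figure for this slope, so there is none to reproduce.

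**Assumptions, not in the documents.** Between-subject SD sb of 15-25 ms and within-subject SD sw of 8-12 ms; median Week 4 concentration of 100-300 ng/mL; CV of 30-50%; zero concentration at Week 24; Weeks 8-16 either on target or at the nearest value the four capsule strengths reach; no dropout. The reference setting is SD 20/10 ms, Week 4 median 200 ng/mL, CV 30%. The QTcF stopping threshold in Protocol 7.5, the one listed rule by which QTcF could feed back on dosing, is ignored.

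**Formulas.** Per subject, V = sw²·I + sb²·J. The slope SE is the square root of the concentration entry of (XᵀV⁻¹X)⁻¹. The bias from a shared trend t is the concentration entry of (XᵀV⁻¹X)⁻¹XᵀV⁻¹t. Conditioning on baseline replaces sb² by sb²·sw²/(sb² + sw²); in the reference setting this is 400 × 100/500 = 80, so the remaining between-subject SD falls from 20 to about 8.9 ms.

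**Step 1: SE of the predicted effect at 500 ng/mL (ms), reference setting**

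| Design | SAP model | + baseline | + baseline + visit |
|---|---|---|---|
| Placebo in, Week 24 in, on target | 1.86 | 1.73 | 2.13 |
| Placebo in, Week 24 in, four strengths | 2.07 | 1.92 | 2.39 |
| Placebo in, no Week 24, on target | 2.84 | 2.30 | 2.44 |
| Placebo in, no Week 24, four strengths | 3.27 | 2.61 | 2.73 |
| No placebo, Week 24 in, on target | 1.85 | 1.79 | 2.72 |
| No placebo, Week 24 in, four strengths | 2.12 | 2.06 | 3.33 |

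**Step 2: gain from baseline.** With placebo and Week 24, 1 − 1.73/1.86 = 7%. Without Week 24, 1 − 2.30/2.84 = 19%. Over all settings the cut is 5-8% and 11-26% with placebo, and 1-4% and 5-13% without. A separate calculation with SD pairs 20/8, 15/10 and 12/12 ms and Week 4 concentrations of 150 or 300 ng/mL found that omitting baseline raises the SE by 3-11% with Week 24 and 7-48% without. As cuts these are 1 − 1/1.03 to 1 − 1/1.11 (3-10%) and 1 − 1/1.07 to 1 − 1/1.48 (7-32%). The direction is stable; the size depends on the assumed variances.

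**Step 3: bias at 500 ng/mL per 1 ms of shared drift (SAP model, placebo in)**

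| Shape of drift | Week 24 in | Week 24 out |
|---|---|---|
| Present on treatment, gone by Week 24 | +0.47 to +1.21 | 0 (constant shift) |
| Linear to Week 24 | −0.14 to −0.48 | not tabulated |
| Linear to Week 16, then flat | −0.30 to +0.03 | +0.02 to +0.93 |
| Step persisting through Week 24 | 0 | 0 (constant shift) |

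With visit as a factor the bias is 0 in every case.

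**Step 4: the visit term's own cost.** This is measured against the baseline model. With placebo and Week 24: 2.13/1.73 = 1.23 and 2.39/1.92 = 1.24, so +23-24%. Without placebo: 2.72/1.79 = 1.52 and 3.33/2.06 = 1.62, so +52-62%. With placebo but no Week 24: 2.44/2.30 = 1.06 and 2.73/2.61 = 1.05.

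**Step 5: simulation.** REML, 500 trials per cell, true effect 10 ms, placebo and Week 24 in, on target. Each cell lists SAP / + baseline / + baseline + visit.

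| Shared drift | Mean estimate | RMSE or coverage |
|---|---|---|
| None | 9.9 / 9.9 / 9.9 | RMSE 1.87 / 1.74 / 2.22 |
| 2 ms on-treatment shift | 11.6 / 11.3 / 10.1 | RMSE 2.50 / 2.28 / 2.18 |
| 2 ms linear | 9.6 / 9.6 / 10.1 | RMSE 1.96 / 1.85 / 2.18 |
| 5 ms on-treatment shift | 13.6 / 13.2 / 10.2 | Coverage 0.52 / 0.57 / 0.95 |
| 5 ms linear | 8.4 / 8.6 / 9.9 | Coverage 0.86 / 0.88 / 0.95 |

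**Step 6: break-even drift.** This is √(SE²(baseline + visit) − SE²(baseline)) divided by the absolute bias per ms in the baseline model. In the reference setting, √(2.13² − 1.73²) = 1.24. For an on-treatment shift the simulated bias is (11.3 − 9.9)/2 = 0.7 per ms, so break-even is about 1.24/0.7 = 1.8 ms. For linear drift it is (9.9 − 8.6)/5 = 0.26 per ms, so about 4.8 ms. Over all settings the ranges are 1.4-2.9 ms and 2.4-9.5 ms. For a persistent step the visit term never pays.

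**The case against.** A reader might infer that a shared trend could not be told apart from a concentration effect. The documents do not support that. SAP 13.2 also summarises QTcF change from baseline at each time point, and SAP 6 presents summaries with placebo in its own column. A common drift would be visible there. What stands is narrower: seeing the drift does not take it out of the slope or its interval.

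A reader might also infer that omitting baseline biases the slope, or wastes the Day 1 ECG altogether. Neither follows. Dose adjustment depends on Week 4 PK and not on QTcF, and the predose ECG feeds the change-from-baseline summaries and the tables of increases above 30 and 60 msec. Only the model leaves it unused.

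The other side has further good points. No trend is indicated anywhere, and every SD, concentration and drift size above is assumed. The random subject effect already absorbs most between-subject variation, so the baseline gain is small when Week 24 is used. The visit model has the worst RMSE when there is no drift. Protocol 12.3 promises a separate PK SAP, and redacted text may add detail, although 13.2 itself is legible. All of this limits the weight of the point and argues against replacing the planned model with a visit-adjusted one. It does not argue against adding the baseline term.

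Placebo handling should not be read as settled by the Safety-population rule. That rule says who is analysed; it does not say that placebo records enter a time-matched concentration regression at zero.

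**Conclusion.** The point holds as a minor one. Leaving out baseline QTcF costs precision without bias: about 5-8% of the slope SE with Week 24 and 11-26% without, placebo in; 1-4% and 5-13% with placebo out. The absence of visit adjustment is a conditional weakness. If a shared trend exists, the slope can be pulled up or down or left unchanged, depending on the trend's shape and on whether Week 24 enters.

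Whether Week 24 is used matters more to precision than the baseline term does: in the reference setting the SAP-model SE is 1.86 ms with it and 2.84 ms without, on target. The silence on Week 24 is missing detail, not a contradiction.

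The stakes are limited. The model is optional, SAP 13 plans no hypothesis tests on safety variables, and the stopping criterion in Protocol 7.5 uses individual QTcF values, not this slope.

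**What to change.** In SAP 13.2:

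1. Add centred baseline QTcF (last predose value) as a fixed effect in the linear model.
2. As a sensitivity analysis, fit the same model with nominal visit as a categorical fixed effect. Report that slope and 95% CI beside the model without visit, not in its place.
3. Show the slope with and without the off-drug Week 24 pairs.
4. State whether placebo records enter, and whether at concentration 0 or at the half-LLOQ value of SAP 6.4.

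This costs a few sentences of text and some extra fits; no new data are needed. A participant with no predose QTcF would drop out of the fit. The main drawback is the visit term's loss of precision with Week 24 in, 23-24% with placebo and 52-62% without in the reference settings, which is why it belongs in a sensitivity analysis.
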